### Potential risks and benefits to the subjects

#### **Benefits:**

To Individual: Patients will likely enjoy using the VR interventions, which are immersive and impressive upon cursory use. We anticipate that patients may report greater satisfaction, pain management, and overall health during the study.

To Society: This is the first study on the use of virtual reality in an Obstetric setting. Knowledge gained could be used to improve patient satisfaction and pain management with care across all hospitals.

**Risks:**

Patients using the virtual reality intervention may experience side effects common to users of VR and individuals who view 3D video, including motion sickness, dizziness, eye strain, headaches, or other visual abnormalities. If patients experience these symptoms, they will be asked to stop using the VR software for 15 minutes, and will be allowed to continue if they agree and wish to proceed. A small number of patients (up to 0.025%) may experience seizures or severe symptoms (e.g., disorientation, nausea, or drowsiness) upon viewing the virtual reality experience. Seizures from flashing light are more common in children and epileptic patients (who are excluded). To minimize this concern further, we have not incorporated flashing lights into the VR experiences. We have also excluded patients who might be at a priori higher risk for seizures including those with hypertensive disorders of pregnancy.

Some patients may find the VR goggles uncomfortable to wear or confining. To date, patients with claustrophobia have not reported discomfort using VR goggles, as they are often used in treatment of that condition. Nevertheless, individuals previously diagnosed with claustrophobia should discontinue use if they feel uncomfortable. A trained study staff member will be on hand at all times to ensure patient safety.

Patients will also be asked questions that some might consider sensitive in nature, such as perceptions of one's own general mental health, distress, and anxiety. These items may make patients feel uncomfortable or embarrassed. Patients are reminded that they can skip any or all questions that make them feel uncomfortable. Also, patient answers will not be entered into the electronic medical record. Patients may be contacted by CSMC mental health professionals if they give concerning answers, but they can refuse care. These interactions will not impact future care received at CSMC.

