### Study Population and Period

The study population will consist of 40 patients: 20 in the VR arm and 20 in the Control arm (see below for sample size calculations).

We anticipate the recruitment and intervention portion of the study to be completed within 12 months.

The Inclusion criteria are as follows:

1. Female
2. >18 years old
3. English-speaking
4. Able to understand the goals of the study and provide informed consent
5. Pregnant with term gestation
6. Nullipara
7. Pain due to contractions rated from 4-7
8. Contractions at least every 5 minutes x 30 minutes preceding

The Exclusion criteria are as follows:

1. Parous
2. Use of medications for pain relief prior to the intervention
3. Use of an epidural
4. Preterm gestation
5. Pain not due to contractions
6. Pain score of 3 or below or 8 or above
7. Preeclampsia with severe features, eclampsia
8. History of epilepsy, dementia, or other neurologic disease that would prevent using VR
9. Sensitivity to flashing light / motion
10. Medical condition predisposing to nausea or dizziness
11. Injury to the eyes, face, neck, or arms that prevents comfortable use of VR hardware or software, or safe use of the hardware (e.g., open sores, wounds, or skin rash on face)

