### Patient Recruitment

Patients will be recruited by three methods. First, their obstetricians will be made aware of the study, given a study flyer, and asked to inform their patients of the ability to try alternative digital pain management options during their labor course. Second, patients will be informed of the availability of the study during their prenatal classes which are offered by the obstetric nurses at Cedars-Sinai. They will be encouraged to contact study staff ([name]) on admission if they are interested in participating. Last, flyers will be present in labor and delivery making patients aware of the study and asking them to inform their nurse who will then inform study personnel ([name]) if they are interested in participating.

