### Pre-Intervention Procedures

The study staff member will arrive at bedside, explain the risks and benefits of the study, and will obtain informed consent. Next, a physician or authorized study staff member will collect blood pressure and pulse data using standard sphygmomanometers in hospital wards, and will ask the patient to report current pain level on a 0 to 10 scale. We will also assess coping (Roberts, 2010) by asking "How are you coping with your labor?" We will also obtain all pain ratings collected and documented in the EHR during the current hospitalization up to 96 hours

before the intervention. Additionally, the study staff member will administer the **Quantitative Patient Survey** -- included at the end of this document and based on the NIH PROMIS Global Health Survey (10 items) and Childbirth Self-Efficacy inventory (15 items).

When a patient expresses interest in the study, she will then undergo randomization to either the VR arm or the Control arm of the study. Group assignments will be maintained inside sequentially numbered, sealed, opaque envelopes. After informed consent, study personnel will then open the assigned envelope and the study treatment will be revealed. Patients, providers, and study personnel will not be blinded to the assigned intervention.

For those patients randomized to VR, the study staff member will explain the use of the Samsung VR goggle set, and thereafter will allow the patient to use the device freely for up to 30 minutes. Intervals of 2-5 minutes is suggested for first-time use, and patients will be to allowed to discontinue it at any time as long as they are not experiencing any discomfort or side effects (dizziness, motion sickness, etc.). The study staff member will be present at all times, and will work with hospital staff as necessary to ensure the patient is receiving appropriate clinical care throughout the duration of the intervention.

For those patients randomized to the Control, the study staff member will explain that their assignment has been to the standard of care for which is no specific dedicated intervention at this time. Rather their intervention will only be further assessment of their pain scores, vitals, and medication use.

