### **Outcomes and Data Collection**

Primary Outcome: Reduction in pain scores from pre- to post-intervention

Secondary Outcome:

1. Duration of use of the intervention
2. Acceptability of the intervention
3. Need for IV pain medication during the intervention
  - a. Time to IV pain medication after the intervention
4. Request for an epidural during the intervention
  - a. Time to epidural use after the intervention
5. Vital sign changes during and after the intervention including heart rate and blood pressure.

Data Collection

1. Baseline maternal demographics
  - a. Name and Medical Record Number (secured and stored separate from all other data below)
  - b. Age
  - c. Race/Ethnicity
  - d. Insurance status
  - e. Gravidity/Parity
2. Admitting diagnosis
3. Obstetric data
  - a. Gestational age
  - b. Induction agents
  - c. Mode of delivery
4. Vital Signs (blood pressure, heart rate) before, during (continuous pulse oximeter and blood pressure measurements every 10 minutes) and after the intervention.
5. Pain scores before and after the intervention. Average Pain Rating during 4 hours before intervention, and Average Pain Rating after intervention (up to 24 hours).
6. Pain interventions including time to first use of IV pain medication and first use of epidural.
7. Responses to **Quantitative Patient Survey** (PROMIS Global Health pre-intervention, and modified Childbirth Self-Efficacy Inventory pre- and post-intervention)

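### The risk section says women with hypertensive disorders of pregnancy are excluded because of seizure risk, but exclusion 7 removes only preeclampsia with severe features and eclampsia.

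*Combined protocol and SAP*

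**What the plan says.** The Risks section (under Potential risks and benefits to the subjects) gives an upper figure for serious reactions to VR: "A small number of patients (up to 0.025%) may experience seizures or severe symptoms (e.g., disorientation, nausea, or drowsiness". It then lists what has been done to reduce the seizure risk. One of those measures is an exclusion: "We have also excluded patients who might be at a priori higher risk for seizures including those with hypertensive disorders of pregnancy". The hypertensive disorders are named as a class, with no limit by type or severity, and the exclusion is presented as already in place.

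The exclusions themselves are listed under Study Population and Period. The entries that bear on seizure risk are:

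- Exclusion 7: "Preeclampsia with severe features, eclampsia"
- Exclusion 8: "History of epilepsy, dementia, or other neurologic disease that would prevent using VR"
- Exclusion 9: "Sensitivity to flashing light / motion"

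**The concern.** The two sections describe different trial populations. Preeclampsia without severe features and gestational hypertension are hypertensive disorders of pregnancy, so by the Risks section these women are out. By the eligibility list they are in. Staff screen from the list, so the list decides who is exposed to VR.

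What is at stake is participant protection. Anyone judging the safety of the trial from the Risks section would believe that a wider group had been removed than the criteria remove. The consent pages are not available, so nothing is claimed here about what participants were told.

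**Working it through.** The main check is a comparison of texts; the only arithmetic is a bound on the size of the risk.

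**Does any eligibility criterion deliver the stated exclusion?** The list has 8 inclusion and 11 exclusion criteria.

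- Exclusion 7 is the only one that concerns a hypertensive disorder. It is limited by severity, so milder preeclampsia and gestational hypertension pass it.
- Exclusion 8 is neurologic and exclusion 9 concerns light and motion sensitivity.
- Exclusion 10, on conditions that make nausea or dizziness likely, is the nearest to a catch-all, but it does not name hypertension.
- No inclusion criterion refers to blood pressure.

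**Does a later step close the gap?**

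- Pre-Intervention Procedures: staff "will collect blood pressure and pulse data using standard sphygmomanometers in hospital wards", but no value bars entry.
- Outcomes and Data Collection: vital signs are recorded before, during and after the intervention, with "continuous pulse oximeter and blood pressure measurements every 10 minutes" during it. The admitting diagnosis is also recorded. These are data items with no eligibility rule attached.
- Justification for record review for recruitment: the obstetrician is asked whether the patient is a suitable candidate. That is a discretionary judgment with no hypertension rule.
- Patient Recruitment: under one route, "flyers will be present in labor and delivery making patients aware of the study and asking them to inform their nurse", who then tells study personnel. That route adds no check for hypertension either.

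A woman with gestational hypertension or preeclampsia without severe features can therefore meet every listed criterion and be randomised to VR.

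**How large is the risk?** Inputs: the ceiling of 0.025% (Risks section) and 20 women in the VR arm (Study Population and Period).

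- Ceiling as a proportion: 0.025 / 100 = 0.00025, or 1 in 4,000.
- Expected events in the VR arm: 20 × 0.00025 = 0.005.
- Chance of at least one: 1 − (1 − 0.00025)^20 = 0.00499, about 0.5%.

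The ceiling covers seizures together with other severe symptoms, so it is not a seizure rate, and it is applied to all 20 women whatever their blood pressure. The documents give no rate for women with milder hypertensive disorders and no indication of how many might enrol. No multiplier is applied and no subgroup figure is derived.

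**The case against.** The strongest reply is that the risk sentence is shorthand. It sits in a narrative paragraph, its subject is women at raised seizure risk, and the hypertensive disorders are given as an example. Exclusion 7 is worded precisely and looks deliberate. On that reading the severe forms are the intended exclusion, no planned protection is missing, and the defect is loose wording in the Risks section. Nothing in the documents shows that VR raises seizure risk in the milder disorders. This reading is plausible and bears on which fix is right. It does not remove the mismatch, because the sentence still states an exclusion that the list does not contain.

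Two further points stand in part. The record-review section explains which items are needed for the inclusion criteria, and it also omits epilepsy and severe preeclampsia, which are certainly excluded. Its silence on hypertension is therefore weak evidence, and the finding does not depend on it. The arithmetic above bounds the overall risk of severe symptoms; it does not measure the effect of this gap, and the number of affected women enrolled could be zero.

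Other safeguards also remain: epilepsy and light sensitivity are excluded, the VR content has no flashing lights, staff are present throughout, and blood pressure is monitored during use. They keep the point minor, but they do not make the safety statement accurate.

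**Conclusion.** The concern holds. As written, the protocol claims a seizure precaution that its eligibility criteria do not provide, and correct use of those criteria would admit women whom the Risks section says are excluded.

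The point is minor. The same criteria govern both arms, so the comparison is not biased and power does not change. The 0.5% figure assumes that the protocol's own ceiling applies equally and independently to all 20 VR participants. The conclusion about the mismatch needs no numerical assumption; it rests only on reading the class named in the Risks section at face value.

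**What to change.** The authors should state which population they intend and make the two sections agree.

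- If the Risks section states the intention, widen exclusion 7 to all hypertensive disorders of pregnancy. This delivers the protection already claimed. The cost is a slightly smaller eligible pool, which cannot be sized because the documents give no prevalence.
- If only the severe forms were meant, narrow the sentence in the Risks section to preeclampsia with severe features and eclampsia. The eligible pool is then unchanged.

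Either is a one-line edit, and neither affects the sample size calculation or the analysis.

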**Data Security and Privacy:**

Data will be abstracted from the EHR by approved staff, and will be transmitted securely to study staff. Staff data collection will be limited to variables mentioned previously. Demographic and clinical data, as well as Qualitative Interview responses will be entered into a secure database and stored on secure servers at CSMC. We will not collect Social Security numbers, and we will use sequential Unique ID numbers to track patients in the study.

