#### **Participating in the Intervention:**

Would you like to participate in a study like this one again? Why?

How did participating in this study make you feel?

(PROBES: distracted, happy, confused, dizzy, anxious, at ease, etc.)

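### The plan names VR side effects but has no structured record of symptoms, pauses or reasons for stopping, and no symptom question for Control, so reliable incidence and a by-arm description are unavailable.

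*Combined protocol and SAP*

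**What the plan says.** **Harms foreseen.** The Risks section lists common VR side effects, "including motion sickness, dizziness, eye strain, headaches, or other visual abnormalities". For women who have them, "they will be asked to stop using the VR software for 15 minutes", after which they may resume. It also says: "A small number of patients (up to 0.025%) may experience seizures or severe symptoms". The examples of severe symptoms given there are disorientation, nausea and drowsiness. Under Pre-Intervention Procedures, a staff member stays with the VR patient throughout.

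**What is to be recorded.** Outcomes and Data Collection has five secondary outcomes. They include "Duration of use of the intervention" and "Acceptability of the intervention"; the only safety-type outcome is change in heart rate and blood pressure. The eight data items are demographics, admitting diagnosis, obstetric data, vital signs, pain scores, pain interventions, survey responses and qualitative interview responses.

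**The interview.** The script asks how taking part made the woman feel, with the note "PROBES: distracted, happy, confused, dizzy, anxious, at ease, etc". It also asks about comfort with the device, concerns, the least favorite part, and perceived effects on anxiety and pain. Post-Intervention Procedures says answers will be written down and coded with qualitative software.

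**Control.** Pre-Intervention Procedures confines follow-up of Control women to pain, vital signs and medication.

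**Analysis.** The text under Sample Size Calculations covers an interview summary and change scores for pain, blood pressure and pulse. It plans no summary of symptoms.

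**Limit on collection.** Data Security and Privacy states: "Staff data collection will be limited to variables mentioned previously".

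**The concern.** The protocol treats these harms as material. It lists them, screens out women prone to motion sensitivity, nausea or dizziness, keeps staff at the bedside and sets a pause rule. Yet nothing tells that staff member to write down that a symptom occurred, that a pause was applied, or why a session ended. Data not collected at the bedside cannot be recovered at analysis.

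Three things are at stake:

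- **Incidence.** The protocol describes itself as the first study of VR in an obstetric setting, so how many women could tolerate the device is a main part of what it can contribute.
- **Attribution.** A woman may feel dizzy or nauseated in labor without a headset. Unless Control women get the same question, there is no background count to set beside the VR count.
- **Two listed secondary outcomes.** Duration of use and acceptability are hard to interpret if a session ended by motion sickness looks the same as one ended by boredom, or if pause time is mixed with wearing time.

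**Working it through.** **Step 1. Match each foreseen event to a place where it would be recorded.**

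| Event in the Risks section | Structured item in Outcomes and Data Collection | Interview prompt |
|---|---|---|
| Dizziness | none | named probe |
| Disorientation | none | nearest probe is confused |
| Motion sickness, eye strain, headache, other visual abnormality | none | none named; general questions on comfort and concerns |
| Nausea, drowsiness, seizure | none | none named |
| 15-minute pause | none | none |
| Reason for stopping | none (duration of use only) | none direct |

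The probe list ends in an open et cetera, so an interviewer may ask about more, but the script does not make her do so.

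**Step 2. Control.** Post-Intervention Procedures does not expressly confine the interview to the VR arm, and the question on how participation felt could be put to anyone. But the script's introduction and most of its questions presuppose having worn the device. There is no Control version, and the Control assessments stated under Pre-Intervention Procedures include no symptom.

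**Step 3. Duration of use.** Take a woman who wears the device for 5 minutes (the upper end of the suggested first interval), pauses for 15, then wears it for 5 more. Wearing time is 5 + 5 = 10 minutes; elapsed time is 5 + 15 + 5 = 25 minutes. Without pause times, either figure could be entered as duration.

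**Step 4. What a count in 20 VR women could show.** Inputs: 20 per arm (Study Population and Period) and the rate of up to 0.025% (Risks). The documents give no rate for the common symptoms, so 5%, 10% and 20% are assumptions.

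Chance of at least one case = 1 − (1 − p)^20:

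- p = 5%: 1 − 0.95^20 = 0.642, or 64%
- p = 10%: 1 − 0.90^20 = 0.878, or 88%
- p = 20%: 1 − 0.80^20 = 0.988, or 99%
- p = 0.025%: 1 − 0.99975^20 = 0.005, or 0.5%

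If no case is seen, the exact upper limit is 1 − 0.05^(1/20) = 13.9% (one-sided 95%), or 1 − 0.025^(1/20) = 16.8% (two-sided 95%).

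**Step 5. What a comparison of 20 with 20 could show.** For x cases against none, the two-sided Fisher p is 2·C(20,x)/C(40,x).

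- x = 4: 2 × 4,845 / 91,390 = 0.106
- x = 5: 2 × 15,504 / 658,008 = 0.047

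So 5/20 against 0/20 is the smallest such split below 0.05. Power, summed over all outcomes of two independent binomials, is 17% for 20% against 5% and 45% for 30% against 5% (assumed rates).

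**The case against.** The best case for the plan is that harms are not ignored. Interview responses are on the data list, dizziness and confusion are named probes, and further questions cover comfort and concerns. The answers are to be coded, so themes from the VR women could be tabulated. Duration of use would show an early stop, and the interview might reveal its cause. All of this stands, so it would be wrong to infer that the trial can report no harms or that nothing countable is recorded. It does not supply a reliable numerator: for symptoms with no prompt, silence in an interview does not mean absence.

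A reader might also take the sentence in Data Security and Privacy as closing the list of variables and barring staff from noting symptoms. The text does not establish that. The sentence follows one on record abstraction, in a privacy section, and the variables it refers to could include symptoms named earlier in the protocol. The gap does not depend on that reading: even if recording is allowed, nothing asks for it.

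It can be said, too, that 20 per arm is too few to compare harms. As a test, that is right (Step 5). It does not remove the value of counts and intervals for common symptoms (Step 4).

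**Conclusion.** The concern holds in a limited form. Symptoms, pauses and reasons for stopping have no structured record, Control women have no symptom question, and no harms summary is planned. Some VR-arm symptoms could appear as coded themes. A reliable incidence, and a description by arm, could not.

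The loss is real for common symptoms. At assumed true rates of 5% to 20%, a checklist in 20 VR women would show at least one case with 64% to 99% probability, and a clean record would exclude rates above 13.9% (one-sided 95%). These figures assume independent women and complete recording.

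Two stronger inferences should be avoided. The 0.025% figure covers severe disorientation, nausea and drowsiness as well as seizures, so on the protocol's own figure all of these are out of reach, not seizures alone. And recording symptoms in both arms would not yield a powered comparison; it would remain descriptive.

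This should be corrected, but it does not affect the validity of the primary pain outcome.

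**What to change.** Add one item to the list in Outcomes and Data Collection: a short checklist of the symptoms in the Risks section, each present or absent, with severity if present. The bedside staff member completes it in both arms, once before the session and once after it. The second checklist should follow the post-session pain score and vital signs, so that it cannot influence the primary outcome.

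For VR women, also record the start and stop time of each pause and the reason for stopping. This records what the protocol already does and changes no clinical rule.

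In the analysis text, state that the number and proportion with any new symptom will be reported by arm, and with any pause or symptom-related stop in the VR arm, with exact confidence intervals and as descriptive only. Word the limit in Data Security and Privacy so that it covers these items.

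The cost is a brief form, a minor amendment, and some extra questioning of women in labor. Prompted questions raise reported symptom counts in both arms. Because assignment is open, they may not raise them equally, which is a further reason to keep the comparison descriptive.
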